## Procedures

Permission from primary teams will be sought on Columbia University Medical Center: New York Presbyterian – Children’s Hospital of New York (CHONY) labor and delivery and informed consent obtained from women willing to participate in the study. Women scheduled for cesarean delivery will be contacted by the research team via 1 of 3 options: 1) via telephone to obtain telephone consent in the week prior to their scheduled procedure; 2) in person at the last outpatient visit prior to their scheduled c-section; 3) in person at the time of admission to labor and delivery for their scheduled procedure if they cannot be contacted beforehand. Women admitted to the antepartum service or labor and delivery for induction of labor or spontaneous labor who then undergo intrapartum cesarean delivery will be consented at the time the decision is made to proceed with cesarean.

Once consent is obtained, randomization will be performed using a computer-generated algorithm. Consenting women will be randomly assigned in a 1:1 ratio to each group by trained research personnel. Women meeting inclusion criteria will be randomized to two groups: 1) experimental arm: Dermabond Prineo skin closure at the time of cesarean section; or 2) control arm: standard subcuticular skin closure at the time of cesarean section. Following randomization, the assigned intervention will be announced to the surgical team at the time of the surgical time-out in the operating room, dictating either standard subcuticular skin closure or closure with Dermabond Prineo, both of which will be available in the Labor and Delivery operating rooms. Those who receive standard subcuticular skin closure will have their incision covered by a standard pressure dressing, as per routine protocol. Those who receive Dermabond Prineo will forego the application of an additional pressure dressing, as one of the benefits of the Dermabond Prineo closure is that an overlying dressing is no longer necessary. Thus, this is an open label trial as both the surgical team and the patient will be able to visualize what type of closure technique was utilized.

In addition to the overall operative time, the total skin closure time will be documented by the surgical staff for all women enrolled in the study. For the standard subcuticular skin closure group, the total skin closure time will include the time the first subcuticular skin suture is placed, to the completion of the pressure dressing application. For the Dermabond Prineo closure group, the total skin closure time will include the time the Dermabond mesh is first applied, to the completion of the removal of the outer adhesive edge once the Dermabond glue dries.

Regardless of group assignment, standard perioperative interventions as part of the perioperative bundle to prevent and decrease the incidence of cesarean section SSIs will be utilized, including the use of chlorhexidine skin prep, hair removal around the surgical site, preoperative antibiotic administration for surgical prophylaxis, vaginal prep for laboring patients, and subcutaneous skin closure with suture for subcutaneous depth of more than 2cm. Labor and delivery management, as well as intraoperative surgical technique, will otherwise be at the discretion of the obstetric care providers. Patients who require stat cesarean delivery with the use of Betadine skin prep, intraoperative cesarean hysterectomy, or vertical skin incision will be excluded from the study.

All patients will receive routine postoperative care. However, postpartum nursing and clinical staff will be educated via in-services on additional postoperative considerations for patients who receive Dermabond Prineo skin closure; namely, that they are able to shower immediately postoperatively as they will not have a postoperative surgical dressing, and that the adhesive should not be removed during their postoperative stay. Otherwise, routine postoperative considerations will apply to both groups, including keeping the incision clean and dry.

Postoperative wound assessment for both groups will occur at 2 separate time intervals: 1) immediate postoperative wound assessment on postoperative day 3 by the surgical team of both the composite primary outcome, as well as postoperative pain scores; 2) postoperative follow up at 4-6 weeks via a telehealth research visit to assess the primary outcome via the Patient Scar Assessment Scale (PSAS) questionnaire.

In terms of immediate postoperative wound assessment on postoperative day 3, a member of the surgical team will perform a standard postoperative wound assessment prior to hospital discharge to assess for evidence of the wound complications, including the presence or absence of superficial SSI, deep SSI, endometritis, and/or wound disruption. Postoperative pain scores are also documented for all patients by postpartum nursing staff as part of routine postoperative care, and will be assessed for patients in both groups.

Long term postoperative follow up will then be assessed by the research team at 4-6 week postoperative follow up visits. Patients will be consented, at the time of initial consent to the study, to a short telehealth video or telephone visit at 4-6 weeks postoperative. This research visit will administer the Patient Scar Assessment Scale (PSAS) questionnaire to assess for our primary outcome of patient scar satisfaction. Additionally, chart review will be performed at this time to assess for the presence of other secondary outcomes, such as wound complication.

The research team will perform chart review to abstract maternal demographics, delivery information, and maternal and neonatal outcomes from maternal and neonatal medical records. This information will be entered into REDCap, a web-based data collection system. Once the study is underway, an interim analysis using the previously described statistical methodology may be appropriate to ensure that there is not a disproportionate incidence of the primary composite outcome or other adverse outcome in the experimental group.

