### **Study Design**

This will be a prospective randomized, open label trial as both surgeons and patients will know what type of closure technique is utilized. Two study groups will be defined as described above. In group 1, Dermabond Prineo will be utilized in place of standard subcuticular closure at the time of cesarean skin closure. In group 2, standard subcuticular closure will be utilized at the time of cesarean skin closure. All patients will be randomized immediately preoperatively as part of the multidisciplinary preoperative briefing process. See procedure below for further details.

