### **Inclusion Criteria**

- Women age 18 years or older
- Admitted to CHONY Labor and Delivery unit

- All women scheduled for primary or repeat cesarean deliveries
- All women undergoing intrapartum or antepartum cesarean delivery
- Pfannenstiel skin incision
- Birth of a live infant at time of cesarean delivery

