#### Exclusion Criteria

- Vertical skin incision
- Cesarean hysterectomy
- Emergency or stat cesarean delivery excluding standard preoperative preparation measures (i.e. use of Chlorhexidine skin prep, vaginal prep, etc)
- Intrapartum stillbirth
- Planned postpartum follow up at another facility
- Contraindications to routine postpartum pain medications
- Allergy to skin glue/adhesive

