As previously described, an interim analysis may be conducted once the study is underway to ensure that there is not a disproportionate incidence of the primary composite outcome or other adverse outcome in the Dermabond Prineo group, although this has not been shown in any prior studies involving this skin closure method. Although unlikely, it is possible that participating in this study may involve risks to the patient that are not expected. No neonatal risks are anticipated as part of this study, as the intervention will occur following delivery.

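### The arm is announced at the surgical time-out but not used until skin closure; opening it just before closure would keep intraoperative exclusions and pre-closure conduct blind to arm at little cost (low priority).

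*Combined protocol and SAP*

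**What the plan says.** **When the arm is set and revealed.** Study Design states: "All patients will be randomized immediately preoperatively as part of the multidisciplinary preoperative briefing process". Procedures adds that "the assigned intervention will be announced to the surgical team at the time of the surgical time-out in the operating room".

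**When the arm is first used.** Study Design has the adhesive replace the suture at skin closure. Potential Risks agrees that nothing arm-specific happens before birth: "No neonatal risks are anticipated as part of this study, as the intervention will occur following delivery". Procedures applies the infection bundle to both arms alike ("Regardless of group assignment, standard perioperative interventions as part of the perioperative bundle"). That bundle includes suturing the subcutaneous layer when it is deeper than 2 cm. Other surgical technique is left to the providers.

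**What can remove a woman after the announcement.** Inclusion Criteria require "Birth of a live infant at time of cesarean delivery" and a Pfannenstiel incision. Exclusion Criteria list vertical incision, cesarean hysterectomy and "Intrapartum stillbirth". Procedures repeats that patients who need "intraoperative cesarean hysterectomy, or vertical skin incision will be excluded from the study".

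**What is measured in that interval.** Secondary Research Questions ask about skin closure time and operative time. Procedures states: "In addition to the overall operative time, the total skin closure time will be documented by the surgical staff".

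The documents give no reason for revealing the arm before closure. They define no analysis set and give no rule for women excluded after randomisation.

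**The concern.** Part of eligibility is settled only during the operation, by a team that already knows the arm. Women who have been randomised can then leave the study with the arm known, and nothing requires those removals to be counted or reported by arm. A reader of the results could not confirm that they were unrelated to allocation.

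The second exposure concerns overall operative time. The closure method cannot act on the minutes before skin closure, but those minutes are part of the outcome and are worked with the arm known. They include steps left to discretion, among them whether to close a subcutaneous layer of 2 cm or less. A difference in operative time could therefore include something other than the closure method.

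Both doubts can be avoided, because the team does not need the arm until the skin is to be closed.

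**Working it through.** **1. Sequence of events**

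| Step | Section | Arm known to team as planned | Arm known if opened just before closure |
|---|---|---|---|
| Preoperative briefing | Study Design | Not stated | No, if concealed there too |
| Time-out | Procedures | Yes | No |
| Incision type, live birth, any hysterectomy before closure | Inclusion and Exclusion Criteria; Procedures | Yes | No |
| Subcutaneous layer (rule above 2 cm, discretion otherwise) | Procedures | Yes | No |
| Skin closure | Study Design; Procedures | Yes | Yes |
| Day-3 assessment, pain scores, PSAS | Procedures | Yes | Yes |

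Late opening changes rows 2 to 4, and row 1 only if the briefing is also covered.

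**2. The plan's own figure.** Sample Size Calculation gives a mean of 20, SD 6, a 20% reduction (0.20 × 20 = 4 points), 80% power, two-sided alpha 0.05 and 20% loss, and states 188 in total. The usual formula gives n per arm = 2 × (1.960 + 0.842)² × 6²/4² = 35.3, so 36. The exact t calculation gives 37. Allowing for loss, 37/0.8 = 46.25, so 47 per arm and 94 in total. The stated 188 is therefore not reproduced; it is twice 94. That is a separate matter, and the shift in step 3 does not contain n.

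**3. Possible shift in PSAS (illustration).** The documents give no rate of intraoperative exclusion, so the following are assumptions: a share x is lost from one arm only, and every woman lost lies D = 6 points (1 SD) from that arm's mean in the same direction. The mean of those remaining moves by x/(1 − x) × D.

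- x = 1% (0.94 of 94 women): 0.01/0.99 × 6 = 0.061 points, and 0.061/4 = 1.5% of the planned difference.
- x = 5% (4.7 of 94 women): 0.05/0.95 × 6 = 0.316 points, and 0.316/4 = 7.9% of the planned difference.

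Equal loss of similar women in both arms gives no bias.

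**4. Against sampling error.** With 94 × 0.8 ≈ 75 evaluable per arm, the standard error of the difference is 6 × √(2/75) = 0.98. The larger shift is 0.316/0.98 = 0.32 of one standard error.

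**5. Power.** If 1-5% of both arms were excluded and 20% of the rest lost to follow-up, 74 to 71 women per arm would remain. Power for 4 points would be about 98% throughout, so power is not the issue.

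**6. Operative time.** The documents give no operative durations or variances, so no size can be attached.

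**7. Workload of late opening.** From Feasibility/Timeline: 30 × 0.90 × 0.50 = 13.5 women a week, and 13.5/7 = 1.9 a day.

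**The case against.** The strongest reply is that no bias mechanism is shown. Hysterectomy, incision type and live birth are observable clinical events that precede the study treatment, and nothing in the documents links them to the closure arm. Removing women for such events does not in itself bias the comparison. This stands. A reader might infer that the PSAS comparison is materially compromised; the documents do not support that, and the calculation above is close to a worst case for the rates assumed.

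Second, the missing analysis-set rule is a gap whenever the arm is announced, and a sentence in the plan could close it without touching the operating room. This also stands. It does not make removals blind to arm, however, and it does nothing for the minutes before closure.

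Third, the trial is declared open label. Procedures rests that on the closure being visible to the team and the patient. This explains knowledge of the arm from closure onward, not before it. Conversely, a reader might infer that late opening would blind the trial. It would not: closure, day-3 assessment, pain scores and PSAS stay open.

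Fourth, the effect on operative time is conjecture, and the new step itself falls inside that outcome. Both are true. No document suggests that surgeons would change pace by arm. Skin closure time has its own start and stop points and is not affected by the early announcement.

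Finally, the low cost is an inference. Both products are said to be available in the operating rooms, but the plan does not cost the step or say who would perform it.

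**Conclusion.** The point holds as a cheap design improvement of low priority. The arm is disclosed earlier than it is needed. Between disclosure and use lie exclusions decided during surgery and discretionary steps that count in a secondary outcome.

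The likely effect on PSAS is very small: 0.06-0.32 points, or 1.5-8% of the planned 4-point difference. That range rests on an assumed 1-5% loss from one arm only, at an assumed 1 SD from its mean. The effect on overall operative time cannot be sized from the documents. The documents do not show that exclusions will differ by arm or that surgeons will alter pre-closure conduct. The case for change is that a small edit removes the question.

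**What to change.** **Study Design and Procedures (randomisation and announcement).** Replace the announcement at the time-out, and bring the briefing sentence into line, with wording such as:

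> The allocation is generated, or is held concealed from the whole surgical team (including at the preoperative briefing) and opened, immediately before skin closure and after any subcutaneous layer, by a named person already in the room. Both products are ready beforehand.

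**Procedures (exclusions).** Add:

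> An intraoperative exclusion is recorded with its reason before the allocation is opened. The arm is added later from the randomisation list, and exclusions are counted by arm. Everyone whose allocation is opened is analysed in the assigned arm.

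If the allocation is generated only at that point, women excluded earlier are logged as not randomised and there is no count by arm.

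**Cost.** The change needs wording in two sections and one short step late in each operation, about 13.5 times a week at the plan's recruitment assumptions. The plan must name who opens the allocation, including for intrapartum cesareans. The step lies inside overall operative time but before the skin closure clock starts; having both products ready keeps any delay the same in both arms. Sample size, alpha and the target difference do not change.

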### **Secondary Research Questions**

1. Does Dermabond Prineo decrease the rate of wound complications after cesarean section when compared to standard subcuticular suture?
2. Does Dermabond Prineo decrease overall skin closure time and operative time at the time of cesarean section when compared to standard subcuticular suture?
3. Is Dermabond Prineo associated with decreased postoperative pain scores after cesarean section when compared to standard subcuticular suture?

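### Skin-closure time runs between product-specific events, with no rule for a converted Prineo closure, so Prineo time may be understated

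*Combined protocol and SAP*

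**What the plan says.** Secondary question 2 asks: "Does Dermabond Prineo decrease overall skin closure time and operative time at the time of cesarean section". Skin closure time and operative time are thus two separate measures under one question.

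The Procedures section defines skin closure time separately for each arm:

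- Suture arm: "the time the first subcuticular skin suture is placed, to the completion of the pressure dressing application".
- Prineo arm: "the time the Dermabond mesh is first applied, to the completion of the removal of the outer adhesive edge", once the glue has dried.

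The same section says that "the total skin closure time will be documented by the surgical staff for all women enrolled in the study", and records this "In addition to the overall operative time". The start and end of operative time are not defined.

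Three further statements bear on the point. Both arms receive "subcutaneous skin closure with suture for subcutaneous depth of more than 2cm". Apart from the listed bundle, "intraoperative surgical technique, will otherwise be at the discretion of the obstetric care providers". Suture and Prineo are "both of which will be available in the Labor and Delivery operating rooms", so changing method during a case is physically possible.

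The documents describe no step for bringing the skin edges together before the mesh goes on. They give no rule for a closure that is converted or reinforced, no analysis method for the time endpoint, and no statement that it is analysed by assigned arm.

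**The concern.** A comparison of durations is fair only if the two clocks cover the same stretch of work. Here each clock opens at the first act of its own product and closes at that product's last act. For suture, the first act already is the joining of the edges. For Prineo, anything done to align, dry or hold the edges before mesh contact happens before the clock opens.

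The end event has a different weakness: it presumes that the product is used to completion. If the mesh is abandoned for suture, the event that stops the Prineo clock never happens. If suture is added after it, the clock has stopped while closure is still going on.

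Where either situation arises, the likely effect is to make Prineo look faster. The background section already reports closure up to 84% shorter, and the budget section says the results will aim to promote the product. Staff who know the assignment record the times, and the surgical teams are trained by in-service in a product the background says has not been used in obstetric surgery. A favourable time difference should therefore rest on a measure that does not depend on the product.

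**Working it through.** **1. Which work each clock captures**

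| Work | Suture arm | Prineo arm |
|---|---|---|
| Preparing the edges before the first act of the method | untimed | untimed |
| Bringing the edges together | timed (it is the stitching) | timed only if done at or after mesh contact |
| Last step of the method | timed (dressing) | timed (drying, then edge removal) |
| Method abandoned for the other one | end event may not occur | end event does not occur |
| Closure redone or reinforced with suture | timed if before the dressing | untimed if after edge removal |

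The first row is common to both arms. The second row is where the start events differ. In the last row, a suture line that is redone still comes before its dressing, so it stays inside the clock. Suture added after the Prineo edge is removed does not.

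**2. What can be computed from the documents**

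The plan gives no mean, SD or conversion rate for closure time, so there is no planned figure to reproduce and the bias cannot be calculated. The only related figures are the background's 60-second drying time and the reduction of up to 84%. The 94 per arm was set for the scar score and is taken as stated. Closure time is recorded in the operating room, so the 20% loss to follow-up does not reduce it.

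**3. Illustration: untimed work before the mesh (assumed values)**

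Assume equal true total times and a net d minutes untimed in the Prineo arm only, beyond any preparation untimed in both arms. Compare means two-sided at 0.05, the level the plan states for the scar score, with n = 94 per arm.

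SE = SD × √(2/94). P(false significant difference) = Φ(d/SE − 1.96) + Φ(−d/SE − 1.96).

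Example, d = 1 and SD = 2: SE = 2 × 0.1459 = 0.292; 1/0.292 = 3.43; Φ(3.43 − 1.96) = Φ(1.47) = 0.93.

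| SD (min) | d = 0.5 | d = 1 | d = 2 |
|---|---|---|---|
| 2 | 40% | 93% | about 100% |
| 3 | 21% | 63% | 99.5% |
| 4 | 14% | 40% | 93% |

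**4. Illustration: conversions (assumed values)**

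If a share c of Prineo closures is converted and e extra minutes each go uncounted, the Prineo mean is too low by c × e.

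- c = 2% (about 2 of 94), e = 5: 0.02 × 5 = 0.1 min.
- c = 10% (about 9 of 94), e = 10: 0.10 × 10 = 1.0 min.

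If instead the converted cases had no recorded time, with 3 minutes for a completed Prineo closure, 15 for a converted one and 5% converted, the mean by assigned arm would be 0.95 × 3 + 0.05 × 15 = 3.6 minutes, against 3.0 without them. The understatement is 0.6/3.6 = 17%.

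**5. Would this reverse a large effect?**

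Take 3 minutes for Prineo and the full 84% reduction. Suture time is then 3/0.16 = 18.75 minutes. Counting the conversions in step 4 gives 1 − 3.6/18.75 = 81%. Adding 5 untimed minutes for every Prineo patient as well gives 1 − 8.6/18.75 = 54%. On these inputs the direction holds and the size shrinks.

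**The case against.** The strongest reply is that most of the harm is conditional.

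- A reader might infer that edge work before the mesh is taking place and being left out. The documents describe no such step. Nor does the sentence leaving technique to the providers clearly license extra skin stitches: it says otherwise at their discretion, and skin closure is the randomised element. This stands, so the loss of pre-mesh time is a possibility and not a finding.
- A reader might infer that failed Prineo closures are excluded or moved to the suture arm. Nothing says so, and a time is to be recorded for every enrolled woman. This also stands: the handling is undefined. But that promise cannot be met under the plan's own definition when the Prineo end event never occurs.
- A reader might infer that only the Prineo clock omits work. Preparation before the first stitch is untimed too, and a suture closure abandoned for Prineo would also lack a rule. This stands. The difference is that joining the edges is always inside the suture clock.
- Overall operative time is recorded and would capture pre-mesh work and conversions. This stands in part. It is undefined, it carries the variation of the whole operation, and the secondary question names skin closure time as a measure of its own.
- The endpoint is one half of one of three secondary questions, and if the true saving is near 84% its direction would survive. This is correct for large effects. Step 3 shows that it does not protect against a false positive when the true difference is small.

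**Conclusion.** The point holds in a limited form. The plan states arm-specific, product-dependent start and stop events, and the Prineo end event does not occur, or does not mark the end of closure, when the mesh is abandoned or reinforced. Prineo skin closure time may therefore be understated on secondary question 2.

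The documents do not support saying that it will be understated, that failed closures are dropped, or that only the Prineo arm has untimed work. The size is unknown. Every number of minutes, SD and conversion rate above is an assumption. Across the assumed ranges, conversions alone lower the Prineo mean by 0.1 to 1.0 minute, and a net 0.5 to 2 minutes of untimed work gives a false significant difference with probability from 14% to about 100%.

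The primary scar-score outcome, the sample size and the safety assessment are unaffected. The change is still worth making, because times not recorded in the operating room cannot be recovered afterwards.

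**What to change.** Amend the timing paragraph in Procedures before enrolment, or early if enrolment has begun:

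- **Start, both arms:** completion of the last layer below the skin (fascia, or the subcutaneous layer when it is sutured). Starting at fascial closure in every patient would bring subcutaneous suturing into a question about skin closure.
- **Stop, both arms:** the skin is finally closed, by whatever method, and any dressing is complete.
- **Converted or reinforced closures, either arm:** time to that same end, record that the conversion or reinforcement took place, and analyse in the assigned arm. This is a measurement rule only; it does not say when a closure should be converted.
- **Current arm-specific interval:** keep it as a descriptive measure.

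The cost is one more clock time for staff who already record times, and a sentence or two of text. The common interval will be slightly noisier, and the apparent time saving may be smaller. No sample-size figure changes.
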